applications. These risks are clearly defined within the Informed Consent Form and discussed with the patient at the outset of participation. Information collected by mobile applications or 'apps' is subject to their terms of use, which each participant should read carefully. Many mobile apps that are developed are intended to be very secure, compliant with federal privacy regulations, and used and tested by other academic centers. However, any mobile app that is downloaded carries potential security risks.

The daily data collected via TRU-BMT will be kept on an EC2 server. AWS EC2 is a tool by Amazon Web Services (AWS) that provides cloud-based compute capacity, allowing developers to run applications on Amazon's computing environment. In the context of the TRU-BMT app, EC2 is the cloud computing machine powering the transfer of TRU-BMT's user-data. Specifically, it houses the logic used by the program to transfer data inputted by the user and collected via the Apple Health kit. EC2 is the "house" that the code that moves data from user phone to dashboard lives in. Only study personnel will have access to the data collected.

Security Measures for AWS:

Security/Access Control: Provider AWS accounts are locked so that they are only able to access the databases that are assigned to them. Authorized users have read-only access to their databases with no ability to access or tamper with any other AWS resources.

Breach: We will enable CloudTrail logs in our AWS account that will constantly generate detailed logs on what activity occurs within the account. **Refer to the Sicklesoft IR plan for actions taken in case of a potential Breach.*

Backups: S3 buckets and databases will have versioning enabled, allowing for recovery if files are accidentally deleted (although this is further mitigated by the providers having read-only access to the buckets/databases). On the AWS end, the data will be stored in at least 3 devices in the region to protect against failures.

HIPAA Compliance: The AWS resources being utilized are certified HIPAA compliant. Additionally, Sicklesoft's AWS account is under the Business Associate Addendum (BAA), which certifies that the AWS account is approved to host PHI data. The Sicklesoft team closely monitors HIPAA guidelines to ensure that all AWS resources are configured in a way that stays HIPAA compliant.

- Other Risks and Protections Specific to the Mobile Application

The TRU-BMT mobile application have been programmed to access only certain features of the participant's device (camera, microphone) that will enable study activities. Other applications on the device will not have access to data entered into the study app.

The SplendoFit app used industry standard SSL encryption. All Google Cloud components used by the platform store data with encryption-at-rest principles (AES256 based). The monitor app runs on a remotely managed iPad which enforces strong user credentials and encrypts the entire file system (using AES256) based on those. Identity platform stores passwords using the bcrypt algorithm. Encryption keys and secrets can be used on the platform to communicate with 3rd parties or create additional layers of encryption within the platform. To protect the content of these keys and secrets, access to them is guarded by only providing certain (service) accounts access to them, using the unified IAM model from Google Cloud. Additional information about security and complicant for the SplendoFit app can be found here: <https://splendo.health/privacy/> .

Patients enrolled in the study will be provided a device (e.g., iPhone, Apple Watch) with the study software. Patients will be instructed to run a current operating system (OS) on their device, review the privacy/security settings often, and restrict any unnecessary access. The application may run in the background of their device. Mobile apps may have unanticipated impact on the operations of the device (e.g., battery drainage). If the patient does not have an unlimited data/text plan, s/he may incur additional charges. At the conclusion of the study, the study team will provide participants with instructions on how to remove the mobile apps from their personal device.

Protocol Summary of: Pro00105683

While these apps are intended to help monitor symptoms, track physical activity and food group intake, provide encouragement to maintain or improve adherence and self-care, the app is not intended to supplant healthcare decisions discussed with the patient's healthcare provider.

As with all technology, we will ask patients and their families to wait until they are in a safe environment, use good judgment, and follow prevailing laws. While the devices are intended to only be used in the participant homes, patients and their families should not perform study-related activities while they are driving.

If a Duke device is used for non-study related reasons, this could add additional personal information onto the device and potentially result in it being sent to unauthorized persons. The Duke-loaned device will be preset with security settings and patients will be asked not alter these during the course of the study. When the device is returned at the end of the study, the device will be cleaned to remove any personal information. If the device is lost or stolen during the course of the study, patients will be instructed to contact the study team immediately.

In order to ensure that patient-reported variables are known to the health care team and research staff, all updates made by the study apps (and other information on the app interface) will be able to be viewed by providers (nurses and physician staff) on a data dashboard.

Participants may have their own personal health information on devices they own for their own personal use independent of this study. This protocol will not require devices to be used in ways that are different from their regular practice but will ask that participants use numerical or alphanumeric codes to unlock the device. The email addresses supplied by the participants for the purpose of this study will also be on the device. The daily data collected will be kept in a server password protected Citrix ShareFile with encrypted WebDAV access to allow two-way communication between participants and providers via the app. Only study personnel will have access to the data collected.

Patients may track their devices via GPS so that the phone can be located once on-line. Moreover, all devices and the website will be password-protected with unique logins and passwords for all personnel on the project, and the website server is protected by a firewall. Medical record login and access fall under the strict policies of the Duke institution. All study personnel will have received Collaborative Institutional Training Initiative (CITI) training to conduct studies involving human subjects. All key personnel are licensed, bondable, healthcare providers.

Other Risks:

Skin Swab – risk of mild discomfort and irritation from skin swabbing, self-limited and will stop on request, minimal risk

Stool Collection – risk of mess with transferring stool sample from hat into collection container, minimal risk

Blood collection – care will be taken to prevent excess blood draw, minimal risk

Relationship of Risks to Benefits: This is a low risk intervention study that does not involve the use of a study drug or investigational device. No adverse health effects had been established from the use of the iPhone or Apple Watch. There is risk of loss of confidentiality, as with any study, and with studies with mobile devices. Treatment-related morbidity is high among HCT patients and mortality ranges from 10-30%. The potential benefit of interventions to increase treatment tolerance is thus substantial. Given the minimal risks associated with the study methods, the risk-benefit analysis is highly favorable.

10. Costs to the Subject

There are no direct costs to subjects.

11. Data Analysis & Statistical Considerations

Study variables will be described using summary statistics and graphical methods. Continuous variables (e.g., 6 minute walk (primary endpoint), AAQ2) will use the generalized linear model with the outcome of interest at year 3 as the dependent variable and treatment assignment as the primary predictor of interest, with a priori selected covariates age, gender, and disease. Ordered categorical outcomes (e.g. Fried Frailty) will use ordered logistic regression models in the same form above. Other outcomes (e.g., length of stay) will be assessed using an adaptation of the Cox regression model [35]. Primary analyses will be followed by examining the extent to which engagement is associated with outcomes using appropriate modeling. We also will explore the trajectory of outcome changes using generalized linear repeated measures models. We will carefully examine model assumptions (e.g., residuals, linearity, influential cases) and reparameterize models accordingly. Assuming an alpha of 0.05 and 10% attrition at 90 days, for the continuous outcomes, a sample size of 60 (20:40) will afford 80% power to detect a standardized group difference of just over 0.8 SDs. This translates to about a 16 meter treatment group difference in the six minute walk test.

12. Data & Safety monitoring

All efforts will be made to insure protection of participant information. All study personnel will complete training on how to appropriately handle data. Hard copy materials (e.g., consent forms) will be stored in a locked cabinet in a locked office of the Clinical Research Coordinator. Data will be stored separately from subject identifiers. Only key personnel will have access to subject identifiers linking to study data. Electronic data will be stored on password protected computers in locked offices, and will be transferred for more permanent storage to secure Duke maintained drives that are backed up every 24 hours.

Any data that are entered by research assistants will be entered twice to cross check and verify accuracy. Questionnaires completed by participants using secure online survey tools will force response with the option to purposely skip a question. All materials will be on an 8th grade reading level to insure understanding of items and personnel will be available to answer participant questions regarding content. Data will be reviewed for completeness and anomalies within 24 hours of collection. The PI will provide regular oversight of all data collection and analysis procedures, meeting weekly with study personnel (Clinical Research Coordinator, Research Assistants). The PI will meet with co-investigators and statistician(s) to review data quality and study progress every other week to once a month as demanded by study tasks. The entire study team will meet within 48 hours in the event that a major data issue is identified that cannot be resolved with individual members of the study team and the PI.

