To analyze the gut microbiome, DNA will be extracted from fecal samples¹ and gut flora bacterial density will be quantified using real-time quantitative polymerase chain reaction (qPCR) as described.² We will amplify 16S ribosomal RNA (rRNA) using Illumina HiSeq platform and analyze the data using the Qiime script package with parallel processing.³ Sequences will be de-noised and clustered at 97% identity using USEARCH and aligned to the 16S rRNA gene, using the align.seqs.py wrapper with the PyNASt algorithm and Greengenes reference alignment. Based on these results, we will calculate diversity (Shannon Diversity, primary endpoint, and Chao1) and construct phylogenetic trees using computational analysis software. We will also make longitudinal evaluations within individual patients.

Blood Collection: Biomarkers, Metabolomics, and Flow Cytometry:

Research blood samples will be collected prior to transplant and Day 14, 30, 90, 180, year 1, year 2, and year 3 post-transplant (year 3 samples will be optional). Research blood samples will include no more than 16ml of blood per collection event (two NaH green top + one EDTA purple top) or 128ml (about 2 fluid ounces) in an 8-week period.

Subjects may be consented to multiple studies that contain the same research blood collection and analysis (specifically Pro00051024, Pro00089697, Pro00092963). If this situation occurs, duplicate research blood samples will not be collected. Instead, data derived from either Pro00051024 or Pro00089697 may be transferred to this study for analysis and reporting purposes.

Research blood samples will be processed as follows prior to biomarker, metabolomics, and flow cytometry analysis:

For Biomarker and Metabolomics analysis:

1. Draw one 4ml lavender top (K₂EDTA) tube.
2. Invert tube 10 times to mix blood.
3. Centrifuge at 4°C at 2500 x g for 15 minutes.
4. Remove plasma from tube and transfer into sterile 15ml conical tube.
5. Repeat centrifuge at 4°C at 2500 x g for 15 minutes.
6. Aliquot ≥1.0ml of plasma equally into 2.0ml cryovials, one for metabolomics, one for plasma biomarkers
7. Freeze at -80°C.

For Flow Cytometry analysis:

1. Draw two green top (Sodium Heparin) tubes.
2. Dilute sample with phosphate-buffered saline (PBS) at a ratio of 1:1.
3. Ficoll sample in accordance with laboratory SOP.
4. For every 1mL of PBMCs (peripheral blood mononuclear cell) collected add 100 µL DMSO (dimethyl sulfoxide).
5. Immediately freeze sample at -80°C.

Metabolomics

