Sensitivity: For the markers of interest, we will establish the Limits of Detection (LOD), Lower Limits of Quantitation (LLOQ) and Upper Limits of Quantitation (ULOQ). LOD is the mean of the zero calibration standards + 2 standard deviations, LLOQ is the lowest calibration standard with back-calculated concentrations having CVs <20% and relative error <25%, and ULOQ is the highest calibration standard with back-calculated concentrations having CVs <20% and relative error <20%.

The Coefficients of Variation (CV): The average %CV will be determined for all markers. The data will be representative of intra-assay variation. In our previous analyses, we have demonstrated that most makers have %CV in the range from 2 -10%.

Assay Specificity: Specific multiplex arrangements will be evaluated for specificity by evaluating: 1) all detection Abs in the well and 2) only the specific detection Ab of interest.

Flow Cytometry

Whole blood samples, will be analyzed and monitored for outcomes such as immune cell differentiation, immune response and development of GVHD. Flow cytometry will be performed -b(7) Briefly, whole blood will be used for isolation of about 1×10^6 mononuclear cells. The mononuclear cells will be incubated with titrated antibodies for 15 minutes at room temperature in the dark. mononuclear cells will be lysed with FACS lysing solution (BD Biosciences, San Jose, CA). Cells will be stained with appropriate antibody cocktail and then analyzed using a FACScanto flow cytometer equipped with FACSDiva software (BD Biosciences). Absolute cells counts will be determined using a Flow-Count Fluorospheres (Beckman Coulter, Brea, CA). Examples of antibodies include: FITC-conjugated anti-CD62L (clone MEL-14), R-PE-conjugated anti-CD45.1 (clone A20), cy-chrome-conjugated anti-CD44 (clone IM7), and their isotype controls (all from BD PharMingen); and FITC-conjugated anti-H-2Db (clone CTDb), PE-conjugated anti-CD4 (clone CT-CD4), B220 (clone RA3-6B2), PE-Texas red-conjugated anti-CD4 (clone RM4-5), tricolor-conjugated anti-CD4 (clone CT-CD4), CD8 α (clone CT-CD8 α), and their isotype controls (Invitrogen, Carlsbad, CA).

For any assessment in which the patient completed as part of their standard of care, we will share that data as part of our analysis for this protocol. We will also review their charts to abstract clinical information on these subjects.

Figure 2. Project Overview and Timeline

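### Bead-based absolute cell counts are taken on isolated mononuclear cells with no stated link to a blood volume, and the two flow cytometry descriptions disagree on the sample

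*Combined protocol and SAP*

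**What the plan says.** Two places in Section 4 describe the flow cytometry sample.

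**Blood Collection: Biomarkers, Metabolomics, and Flow Cytometry.** The steps are introduced with "Research blood samples will be processed as follows prior to biomarker, metabolomics, and flow cytometry analysis". For flow they are, in order:
- "Draw two green top (Sodium Heparin) tubes"
- "Dilute sample with phosphate-buffered saline (PBS) at a ratio of 1:1"
- "Ficoll sample in accordance with laboratory SOP"
- "For every 1mL of PBMCs (peripheral blood mononuclear cell) collected add 100 µL DMSO (dimethyl sulfoxide")
- "Immediately freeze sample at -80" °C

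The only other research tube is a 4 ml EDTA tube, which is spun for plasma. Each collection is capped at 16 ml.

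**Flow Cytometry.** This subsection begins "Whole blood samples, will be analyzed and monitored for outcomes such as immune cell differentiation", and adds immune response and GVHD as further outcomes. It then has about 1×10^6 mononuclear cells isolated from whole blood, stained and run on the cytometer. It closes the method with the counting rule: "Absolute cells counts will be determined using a Flow-Count Fluorospheres (Beckman Coulter, Brea, CA"). The end of the same subsection allows clinical information to be abstracted from charts.

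**The concern.** Counting beads give the number of cells in the suspension they are added to. To turn that into cells per volume of blood, one must know the blood volume behind the suspension, and either no cells may have been lost on the way or the recovery must have been measured. The plan places isolation of a set quantity of mononuclear cells ahead of the count and states none of these quantities. The processing list adds freezing and, by implication, thawing.

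What is at stake is the meaning of a stated laboratory result. A reader of the eventual report would naturally take an absolute count in transplant patients to describe their blood. Followed as written, the method yields a property of the prepared aliquot, and comparisons between patients or visits on that scale could mislead.

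**Working it through.** The documents give no sample size, unit or expected value for flow cytometry, so there is no figure to reproduce. The check compares the texts and then adds an illustration on assumed values.

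**Step 1: is there any reading under which the beads see unseparated blood?**
- *Banked cells.* Under the processing list, the material is Ficoll-separated, mixed with DMSO and frozen. The count would follow separation and thaw.
- *Fresh blood, as the Flow Cytometry subsection opens.* Mononuclear cells are still isolated before staining and counting. The count would follow separation.
- *Beads in a separate whole-blood aliquot.* Neither place describes one. Both heparin tubes are assigned to Ficoll and freezing, and the EDTA tube to plasma.

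Under each described reading the count comes after separation. The 1:1 dilution alone would not matter, since it is a known factor.

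**Step 2: what if the quantity stained is about the same for every sample?** (Assumption; see the objection.)

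Bead count = subset share × cells stained. With an assumed 30% share and 1×10^6 cells, this is 0.30 × 1,000,000 = 300,000 in every case:

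| Assumed mononuclear cells/µL | True subset count/µL (× 0.30) | Bead count | Blood holding 10^6 cells at full recovery |
|---|---|---|---|
| 200 | 60 | 300,000 | 5.0 ml |
| 500 | 150 | 300,000 | 2.0 ml |
| 2,000 | 600 | 300,000 | 0.5 ml |

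A tenfold difference (60 versus 600) disappears.

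**Step 3: are there enough cells to reach one million?** Heparin blood is at most 16 − 4 = 12 ml.
- At 200/µL: 200 × 12,000 µL = 2.4 million cells.
- At 2,000/µL: 24 million cells.
- Recovery = Ficoll recovery × thaw recovery. With assumed ranges of 40–100% and 50–100%, it runs from 0.4 × 0.5 = 20% to 100%.
- Low-count sample: 2.4 × 0.20 = 0.48 million up to 2.4 million. It falls short of one million when recovery is below 1/2.4 ≈ 42%.
- High-count sample: 24 × 0.20 = 4.8 million at worst, so always enough.

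At the worst recovery for the low-count sample, the bead counts would differ by 1.0/0.48 ≈ 2.1-fold. The true tenfold difference would therefore read as about 1- to 2.1-fold.

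**Step 4: what if input is not fixed and the blood volume is known, but losses are not corrected?** The apparent count is then 20% to 100% of the true count on the same assumed recoveries, and may vary from sample to sample.

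**The case against.** The best reply is that the text is a summary. The flow method is given in brief, Ficoll handling is deferred to a laboratory SOP, and either that SOP or a fuller method could record blood volume, yield and post-thaw recovery. This stands in part: the documents show that the link to blood volume is not stated, not that the laboratory could never supply it. But the SOP is cited only for the separation step, and the protocol's own sequence still puts the count after isolation.

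A reader might also infer three stronger things that the documents do not support.
- *That every staining tube is loaded with the same number of cells whatever the patient's count.* The text speaks only of isolating about 10^6 mononuclear cells. Fixed input is plausible but inferred, so Steps 2 and 3 are conditional.
- *That a planned immune-recovery time course would be wrong.* No unit per volume of blood is given, and no analysis of absolute counts over time is specified.
- *That trial results are threatened.* Flow cytometry is absent from the aims and the hypothesis, from the primary outcomes under Measures in Section 4, and from Section 11, where the power statement is expressed in the six-minute walk.

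It may further be said that subset percentages are not safe either, because Ficoll and freeze-thaw can lose cells selectively. That is right, and it limits the fix.

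**Conclusion.** The point holds as a contradiction about the sample plus a counting rule that does not deliver what its name suggests. As written, the bead count measures cells in the suspension and cannot be read as cells per volume of the patient's blood. This does not depend on freezing, because the Flow Cytometry subsection alone already isolates cells before counting.

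The size is uncertain. That differences in blood counts would be largely hidden rests on similar numbers of cells being stained for each sample. The tenfold-to-roughly-twofold figure and the 20–100% range rest on assumed counts and recoveries, none of which the documents give. The consequence is confined to an exploratory assay. The primary outcomes and power are unaffected.

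**What to change.** 1. Reconcile the Blood Collection list and the Flow Cytometry subsection, stating whether flow is run on fresh whole blood, fresh mononuclear cells or thawed mononuclear cells.
2. Remove the bead-count statement for separated or frozen cells, and report subset percentages from them.
3. Where an absolute count is wanted, choose one of two routes:
   - Multiply the percentage by the lymphocyte or mononuclear count from the clinical blood count closest to the draw, abstracted from the chart where available. The percentage must use the same denominator as the clinical count. Record the interval between the two.
   - Use beads only on a measured volume of fresh whole blood, set aside before dilution and separation. This has to be arranged before each draw, since a frozen sample cannot restore the link.

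The cost is a wording change plus, for the first route, abstraction of one blood count per draw; chart review is already allowed. The downsides should be stated in the protocol. The clinical count has its own error, which is large when counts are very low. Selective loss in Ficoll and freeze-thaw may bias the percentages. Some draws may have no matching clinical count, since Table 1 does not list one; those should be reported as percentages only.

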Aim 2. Evaluate the preliminary efficacy of ACTivate in improving physical function and other outcomes in HCT patients (NIH Stage IB). As standard of care, all HCT patients undergo comprehensive functional evaluation (physical, cognitive, mental health, nutrition, social/financial, global, and quality of life) between sign-off (~10 days before HCT) and year 3. This will allow us to compare outcomes in the nine patients in Aim 1 plus an expansion cohort of 11 patients receiving the final iteration of ACTivate (total n=20) to contemporaneous controls matched for age, gender, and disease.

H1: Patients receiving ACTivate will have a shorter hospital stay and better physical function (six-minute walk, primary endpoint) at year 3.

3. **Background and Significance**

Allogeneic hematopoietic stem cell transplant (HCT) has the potential to cure patients with hematologic malignancies and other diseases, but treatment is arduous and there is significant risk of treatment-related morbidity and mortality. Worse clinical outcomes are predicted not only by advanced chronological age, but also by modifiable behavioral factors such as decreased physical function and comorbid psychological conditions, such as depression. Targeted interventions to reduce physical and psychological vulnerabilities during the pre-HCT time period could therefore improve treatment tolerance and HCT outcomes.

ACT [1] is a transdiagnostic, mindfulness-based treatment that has been effective in reducing psychological distress and symptom interference in a variety of clinical populations [2-5], including individuals with cancer [6-15]. Unlike more traditional cognitive-behavioral therapy (CBT), which focuses on changing thoughts/feelings themselves, ACT emphasizes psychological acceptance: voluntarily adopting an open, receptive posture with respect to moment-to-moment experience. This may be well-matched to individuals with cancer for whom distressing thoughts/feelings may not be illogical or irrational, but rather perfectly normal or expected responses to having a life-threatening illness (and embarking on a journey that could cure their disease but could also cause death), or simply inevitable during the course of treatment.

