Measures. Measures are outlined in Table 1. The majority of the assessments are collected as part of routine HCT procedures or tracked in the Duke Adult Bone Marrow Transplant (ABMT) database. Assessments that are not typically collected during HCT procedures have been marked with an (*). Primary outcomes will be the 6-minute walk and length of hospital stay. Target engagement (process of change) will be assessed with the Valuing Questionnaire (VQ) (or equivalent), administered to the patient and the caregiver every 2 weeks for the first 30 days, and once a month thereafter.

ACTivate sessions will be conducted in person or via the Duke extended care platform used for telehealth visits. Participants will also receive reminders of concepts from sessions and reinforcement or prompting from the study team via the custom HCT app (e.g., “Great job completing your steps yesterday!”). All sessions will be audio taped for fidelity review. Fidelity will be assessed with the ACT Measure (ACT-FM), along with an ACTivate protocol checklist (developed after finalization of the protocol in Aim 1). Session tapes from the second interventionist will be reviewed by [name] for ongoing training/consultation to maintain fidelity to the intervention.

Participants’ functional outcomes at Day 30 and Day 90 will be compared to age, gender, and disease-matched controls (case-control design), collected as standard of care.

Use of previously collected data: If a subject is simultaneously on another study and the same assessment or sample is required for both studies, we will only collect once and share the data between studies to avoid subjects having to duplicate efforts.

5. Selection of Subjects

Protocol Summary of: Pro00105683

Eligibility criteria: (1) Over the age of 18 (2) undergoing allogeneic HCT for any cancer or non-cancer illness, (3) English-speaking (4) has a caregiver who is willing to participate. Caregiver eligibility criteria: (1) Over the age of 18 and (2) English-speaking.

6. Subject Recruitment and Compensation

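### The primary outcome is defined two ways: Section 4 makes the six-minute walk and length of stay both primary, H1 and Section 11 give that label to the walk alone, and no rule says what counts as success.

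*Combined protocol and SAP*

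**What the plan says.** - **Section 4, Measures:** "Primary outcomes will be the 6-minute walk and length of hospital stay". Two outcomes, with no order between them.
- **Section 2, Aim 2, H1:** treated patients are predicted to have a "shorter hospital stay and better physical function (six-minute walk, primary endpoint) at year 3". Both outcomes are in the hypothesis, joined by *and*, but only the walk carries the label.
- **Section 11, model for continuous outcomes:** "Continuous variables (e.g., 6 minute walk (primary endpoint), AAQ2) will use the generalized linear model". The walk is again the one marked primary.
- **Section 11, length of stay:** "Other outcomes (e.g., length of stay) will be assessed using an adaptation of the Cox regression model". It is grouped with the remaining outcomes and has no significance level or power of its own.
- **Section 11, power:** "Assuming an alpha of 0.05 and 10% attrition at 90 days, for the continuous outcomes". This is the only place where a significance level is given. No split, testing order or multiplicity adjustment appears anywhere.
- **Section 4, Skin swab and Microbiota Assessment:** the label appears once more, in "we will calculate diversity (Shannon Diversity, primary endpoint, and Chao1".

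The time point of the walk also varies. It is year 3 in H1 and in the Section 11 model. The Section 4 Measures text compares functional outcomes with matched controls at Day 30 and Day 90. The power statement assumes attrition at 90 days.

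**The concern.** A reader of Section 4 would report two primary results, and a reader of Section 11 would report one. Both could claim to follow the plan. The success rule that would reconcile them is missing.

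This matters more here than it would in a blinded randomized trial. Every participant receives the intervention and is compared with matched, non-randomized controls, so group membership is open. Length of stay will ordinarily be known long before a year-3 walk. If the walk turned out null or incomplete, Section 4 would let length of stay be presented as a primary result. If the walk were positive and length of stay were not, Section 11 would let length of stay be set aside. What is at stake is whether the main claim is fixed before the data are seen.

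**Working it through.** **Inputs.** From Section 11: alpha 0.05, 80% power, 60 patients split 20:40, and 10% attrition, taken as 18:36 evaluable. The plan does not state sidedness; two-sided is assumed because it reproduces the plan's figure. The correlation between the two test statistics is not given, so a range is shown.

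**1. The plan's own figure.** The detectable difference in SD units is (z for alpha + z for power) × √(1/n₁ + 1/n₂).
- √(1/18 + 1/36) = 0.2887.
- (1.960 + 0.842) × 0.2887 = 0.809 SD by the normal approximation; 0.824 SD by the noncentral t.
- Reverse check: 0.82 SD at 1:2 needs 18 + 36 = 54 patients, and 54/0.9 = 60.

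This agrees with the stated value of just over 0.8 SD. One-sided 0.05 gives 0.72–0.73 SD, and no attrition gives 0.77–0.78 SD, so neither fits. Applying attrition to the treated group only (18:40) gives 0.81 SD by the t calculation, which also fits; nothing below turns on that choice. The power statement is therefore sound for one continuous outcome tested at 0.05.

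**2. Error under each possible success rule, with no true effect on either outcome and each test at 0.05.**

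| Rule | Chance of a false claim |
|---|---|
| Walk alone | 5% |
| Both required | 0.05² = 0.25% if independent; 2.2% at correlation 0.8 |
| Either suffices, independent | 1 − 0.95² = 9.75% |
| Either suffices, correlation 0.3 | 9.5% |
| Either suffices, correlation 0.5 | 9.1% |
| Either suffices, correlation 0.8 | 7.8% |

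The correlated rows use a bivariate normal distribution for the two statistics. Whatever the dependence, the either rule cannot exceed 0.05 + 0.05 = 10%. If only one of the two effects is null, the both-required rule is still bounded by 5%.

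**3. Cost of an equal alpha split, if both outcomes stay primary.** At 0.025 each, the overall error is 1 − 0.975² = 4.94% if independent, and at most 5%. The detectable walk difference becomes (2.241 + 0.842) × 0.2887 = 0.89 SD by the normal approximation, or 0.91 SD by the t. Put the other way, power at 0.82 SD falls from 79.6% to 70.2% (t).

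**The case against.** The strongest reply is that this is inconsistent wording in a preliminary-efficacy pilot. There are 20 treated patients and non-randomized controls, so the p-value is not a confirmatory 5% test in any case. The analysis section, which should govern, has one primary endpoint, and under it there is no inflation. H1 uses *and*, which does not point to an either-suffices rule. Much of this stands. It limits how serious the point is, and it rules out three stronger readings.

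- **A reader might infer that the plan runs a false-positive risk of about 10%.** It does not follow. No sentence lets either outcome carry the claim, and 0.05 is stated only in the power sentence for continuous outcomes. Length of stay has no stated level at all, so the 9.75% is conditional on a rule the plan never adopts.
- **A reader might count Shannon diversity as a third efficacy test.** Its label sits inside the microbiome methods, where it ranks that measure ahead of Chao1. No treatment-group test of it is described, and no stool sampling from controls. It is outside the efficacy error family.
- **A reader might say that the 80% power fails if both outcomes are required.** That power was stated for a standardized difference in a continuous outcome, and it reproduces. It was never a joint-success claim. Joint power cannot exceed the walk's power, but its value cannot be computed because the plan gives no power for length of stay.

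What the reply does not remove is the contradiction. The plan itself uses primary outcomes, an alpha and a power calculation, so it should say which outcome they apply to. Nothing states that Section 11 overrides Section 4.

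**Conclusion.** The concern holds as an inconsistent definition of the primary outcome with no success rule. Two sections of current text give incompatible answers on length of stay, and no other text settles the matter. It should be corrected before outcome data are examined.

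The consequence for error is conditional. It is at or below 5% if the walk stands alone or both outcomes are needed, and 7.8% to 9.75% (correlation 0.8 down to 0) if either could suffice. The figures assume two-sided tests at 0.05 for both outcomes, and the plan does not confirm this for length of stay. The shifting walk time point is part of the same weakness: one named outcome with several candidate times would still leave room for selection.

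**What to change.** Replace the Section 4 sentence with wording such as: *The single primary outcome is the six-minute walk at [one stated time point], tested at two-sided 0.05. Length of hospital stay is the first secondary outcome. It is tested only if the walk is significant, and is otherwise reported as an estimate with a confidence interval.*

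In the same edit:
- Use one walk time point in H1, Section 4, the Section 11 model and the power statement. If it is year 3, the 90-day attrition assumption must be revisited and the power restated.
- Describe Shannon diversity as the main measure of the microbiome analysis only.

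The cost is a few sentences. Naming the walk as sole primary does not by itself change the power calculation. The downside is that length of stay cannot carry the claim alone.

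If the sponsor prefers two primary outcomes, that also resolves the contradiction, provided the rule is written down. The rule could require both, or split alpha at 0.025 each, with the detectable walk difference then about 0.89–0.91 SD. In either case the power should be restated, including a figure for length of stay.
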